11.2.3. Assessment of participant adherence with study treatment

The behavioral interventions being evaluated target participant treatment adherence.

At each on treatment study visit (every 4 weeks for 12 weeks [or 24 weeks] total), participants will be asked to self-report adherence using a visual analogue scale.

Participants will be asked to return their empty pill bottles at which time the number of pills remaining will be counted.

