Sensitivity Analyses. The Statistical Analysis protocol describes several sensitivity analyses to account for study site differently and to account for covariates that are differentially distributed by arm or are prognostic for the outcome. Additionally, we will conduct additional analyses of the primary outcome to account for missing data/nonadherence related to the primary outcome. Of interest is estimating the most beneficial effect of the higher intensity intervention as if everyone fully complied and there were no losses to follow-up or nonadherence to the intervention. Therefore, missing data will result from persons who do not complete the SVR visit within the window including both those who are lost to follow-up before and after treatment completion. We will conduct an additional per protocol analysis which will exclude individuals who are alive but lost to follow-up (i.e., do not complete the SVR visit) but account for the informative lost to followup using inverse probability censoring weights. Further, we will include the randomization to the different intervention arms as an instrumental variable. An instrumental variable analysis estimates the "complier" average treatment effect. Therefore, by using the randomization as an instrumental variable for the treatment arms, we would be able to estimate the complier treatment effect for those that fully comply with the intervention. A second approach will use fully specified conditional specification multiple imputation of the SVR outcome based on only two variables: treatment completion and adherence. In this analysis, undetermined SVR due to death will not be imputed; deaths will be treated as SVR failures. Additionally, assessing the relationship of the treatment arms with lost to follow-up is of interest in and of itself. This is because as an implementation strategy, policy makers would need to know the potential for loss to a program that they are implementing. Therefore, a time to lost to follow-up analysis will be examined using standard survival methods and accounting for prognostic score.

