STATISTICAL ANALYSIS PLAN

A precision randomized trial to evaluate the impact of tailored hepatitis C virus (HCV) treatment adherence support on HCV treatment outcomes in HIV/HCV co-infected and HCV mono-infected people who inject drugs (PWID) in India

NCT04652804

Supporting Treatment Outcomes among PWID (The STOP-C Study)	
	-
	Funded by:
	onal Institute of Allergy nfectious Diseases
R01-Al-145555-01 Industry Support Provided by:	
Protocol Chair/Co-Chair:	[name] MPH, Co-Chair [name] [name] MPH, Co- Chair
DAIDS-ES Document Number:	DAIDS-ES ID 38666
Version Number:	1.0
Version Day Month Year:	5 January 2024

SIGNATURE PAGE

I agree to conduct the analysis in accordance with the relevant, current protocol.

I agree to personally conduct or supervise the analysis.

Co-Principal Investigator: [name] MPH / Professor

Signed:

Date: 1/5/24

Co-Principal Investigator: [name], PHD MPH / Professor

Signed: Date: 1/5/24

1. Primary outcome

The primary outcome is sustained virologic response (SVR) defined as HCV RNA < lower limit of quantification (LLOQ) 10 – 60 weeks after completion of treatment (cure). The primary analysis will be intention to treat and will be stratified by the risk of treatment failure (minimal and elevated).

The primary analysis will compare the proportion achieving SVR across level of support (low, medium, high intensity) within the two strata of risk (minimal and elevated) independently. Using log-binomial models (or their extensions, i.e., Poisson regression with robust variance estimation) including adjustment for site as a fixed effect, in the elevated risk stratum, we will compare the proportion achieving SVR in those who received the low and moderate intensity interventions (in separate models) to those who received the high intensity intervention resulting in a relative risk (RR). Analysis will be repeated for the minimal risk stratum except comparing those who receive the high and moderate intensity interventions to the low intensity intervention.

Primary comparisons will be intention to treat. That is, the study population for this analysis will include everyone who was randomized. Individuals with missing data on the outcome of interest either due to loss-to-follow-up or death will be treated as failures.

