complete the SVR visit within the window including both those who are lost to follow-up before and after treatment completion. We will conduct an additional per protocol analysis which will exclude individuals who died prior to SVR assessment and who are alive but lost to follow-up (i.e., do not complete the SVR visit) but account for the informative loss to follow-up using inverse probability of censoring weights. Further, we will include the randomization to the different intervention arms as an instrumental variable. An instrumental variable analysis estimates the "complier" average treatment effect. Therefore, by using the randomization as an instrumental variable for the treatment arms, we would be able to estimate the complier treatment effect for those that fully comply with the intervention.

- A second approach will use fully conditional multiple imputation of the SVR outcome based on only two variables: treatment completion and adherence. In this analysis, undetermined SVR due to death will not be imputed; deaths will be treated as SVR failures.
- Assessing the relationship of the treatment arms with loss to follow-up is also of interest in and of itself. This is because as an implementation strategy, policy makers would need to know the potential for loss to a program that they are implementing. Therefore, a time to lost to follow-up analysis will be examined using standard survival methods and accounting for prognostic score.
- **1c. Non-inferiority analyses**. While the overall trial is designed to assess superiority, if there is a failure to identify that one support intervention is superior to another in the minimal risk stratum, sensitivity analyses will examine non-inferiority within this stratum. Non-inferiority is of interest in this case because it is possible that the additional interventions confer no benefit beyond what is offered by the low intensity intervention among those at minimal risk of failure this has important implications for costs and programs. The non-inferiority margin is 5% which is also clinically meaningful.

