- **1d. Subgroup analyses**. Subgroup analyses will explore whether the effect of the intervention in either risk stratum varies by the prognostic score itself as well as by other covariates of interest including age, employment status, HIV status and treatment, drug use, injection drug use, alcohol use, homelessness, depressive symptoms, medication for opioid use disorder (MOUD), distance to study site, readiness for HCV treatment and study site. Interactions will be included in regression models that also adjust for site.
- **1e. Exploratory analyses**. Using viral sequence analysis of baseline and SVR samples, we will reclassify persons with evidence of reinfection (vs. treatment failure) as having achieved SVR. The primary outcome and sensitivity analyses by arm within strata described above will be repeated after this reclassification. We will also conduct exploratory analyses to explore correlates of HCV treatment failure and reinfection overall and by HIV status.

2. Secondary outcomes

Secondary outcomes are 1) treatment completion defined as completing the prescribed course of treatment (12/24 weeks); 2) adherence; 3) reinfection defined as testing positive for HCV Core Ag after achieving SVR; and 4) HIV viral suppression defined as HIV RNA<LLOQ.

2a. Treatment completion.

Those who discontinue treatment prior to the end of their prescribed course will be considered as failures for this analysis. In the elevated risk stratum, using log binomial regression models (or their extensions, i.e., Poisson regression with robust variance estimation), including adjustment for site as a fixed effect, the proportion completing treatment in those who received the low and moderate intensity interventions will be compared to those who received the high intensity intervention (in separate models) resulting in a relative risk (RR). For those at minimal risk of failure, analyses will be similar except comparing the high and medium intensity interventions to the low intensity interventions.

2a.1.Sensitivity analyses.

- Regression models will be repeated considering site as a random effect (instead of as a fixed effect).¹
- Regression models will be repeated without adjustment for site.
- To account for covariates that are differentially distributed by arm or prognostic for the outcome:

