 - We will repeat the regression models described above adjusting for any baseline demographic and behavioral factors that are significantly different by study arm within strata of risk.
 - We will repeat the regression models described above including a covariate for the prognostic score.
 - We will incorporate the covariates included in the prognostic score through application of the standardized estimator of Moore and van der Laan^{2,3} in the stratified analyses (minimal and elevated). This will allow us to estimate the average treatment effect (ATE) within strata contrasting the proportion of the population that would achieve SVR in the groups of interest.
- 2a.2. Non-inferiority analyses. While the overall trial is designed to assess superiority, if there is a failure to identify that one support intervention is superior to another in the minimal risk stratum, sensitivity analyses will examine non-inferiority within this stratum. Non-inferiority is of interest in this case because it is possible that the additional interventions confer no benefit beyond what is offered by the low intensity intervention among those at minimal risk of failure this has important implications for costs and programs. The non-inferiority margin is 5% which is also clinically meaningful.
- 2a.3. Subgroup analyses. Subgroup analyses will explore whether the effect of the intervention in either risk stratum varies by the prognostic score itself as well as by other covariates of interest including age, employment status, HIV status and treatment, drug use, injection drug use, alcohol use, homelessness, depressive symptoms, medication for opioid use disorder (MOUD), distance to study site, readiness for HCV treatment and study site. Interactions will be included in regression models that also adjust for site.

2b. Adherence.

Adherence will be defined both using both self-reported data and objective data on refills completed and pill counts. It will be analyzed as both a continuous outcome (e.g., percentage of doses reported as taken; percentage of doses taken according to refills completed/pill counts) and a dichotomous variable (e.g., >90% of doses reported as taken; >90% of doses taken according to refills completed/pill counts). For the dichotomous adherence outcome, analyses will be conducted as they are specified for the primary outcome using log binomial regression models or

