Additional exploratory analyses will evaluate the impact of non-adherence and delays in completing treatment on SVR. Initial analyses will incorporate data from all three arms. Two variables will be calculated: 1) the percentage of doses completed (as described above); and 2) days to treatment completion. While the scheduled course of treatment will be 84 days for most, participants will be instructed to take all of the doses prescribed (even if doses are missed and the total time for treatment completion extends beyond 84 days). In separate models, log-binomial models (or their extensions, i.e., Poisson regression with robust variance estimation) will be used to estimate the association between 1) estimated adherence and SVR; and 2) days to treatment completion and SVR. These analyses will be combined across risk strata and treatment arm but these variables will be included as covariates. Additional analysis will be conducted exclusively among participants assigned to Arm 3 (high intensity support) where weekly adherence data will be collected using biometric data.

3e. Estimation of heterogeneity in treatment effect and estimation of average treatment effect.

Additional analyses will be completed to estimate heterogeneity in treatment effect and the average treatment effect for the primary (SVR) and secondary outcomes defined above.

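### The multiple-imputation check on SVR leaves randomised arm (and site) out of its imputation model, which can modestly bias the arm contrast in that one sensitivity analysis; adding both is a cheap improvement

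*SAP*

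**What the plan says.** SAP 1b, under missing data and non-adherence, gives the rule: "A second approach will use fully conditional multiple imputation of the SVR outcome based on only two variables: treatment completion and adherence". Deaths are not imputed and stay as failures. Protocol 15.7.2.1 carries the same restriction: "multiple imputation of the SVR outcome based on only two variables: treatment completion and adherence". Neither document says that the imputation is run by arm or by site.

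The analysis that receives the imputed data is wider. SAP section 1 compares SVR "across level of support (low, medium, high intensity) within the two strata of risk (minimal and elevated) independently", and its model is described as "including adjustment for site as a fixed effect, in the elevated risk stratum, we will compare the proportion achieving SVR". Adherence, one of the two predictors, is specified in SAP 2b: "Adherence will be defined both using both self-reported data and objective data on refills completed and pill counts".

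On risk stratum, SAP 1e refers back to the checks in these words: "The primary outcome and sensitivity analyses by arm within strata described above will be repeated after this reclassification". With SAP section 1, this points to working within strata, although the imputation sentence does not repeat it.

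**The concern.** An imputation model should contain at least what the analysis model contains. The word limiting it to two variables is an explicit exclusion, not silence, and the reference to fully conditional imputation names an algorithm without adding predictors. With arm left out, two people with the same recorded completion and adherence get the same predicted SVR whatever their arm. Any arm effect that the two recorded variables do not transmit is therefore absent from the imputed outcomes. Adherence is partly self-reported, so some error in recording it is likely.

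The stake is limited but real. The primary analysis counts every missing SVR as failure, and this check shows what happens when that rule is relaxed. The SAP's inverse-probability-of-censoring analysis is labelled per protocol and excludes deaths. The imputation check keeps deaths as failures, so among the listed missing-data analyses it lies closest to the intention-to-treat population. An avoidable shrinkage could make the effect look less robust than it is.

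**Working it through.** **Anchor from the plan.** Protocol 15.4, elevated stratum of 1,500 (750 high, 500 medium, 250 low), comparator SVR 85%, two-sided alpha 0.05, 80% power. A pooled-variance two-proportion test gives detectable relative risks of 1.075 (high v low) and 1.062 (high v medium). These match the stated 1.08 and 1.06 to rounding. The planning contrast is thus 0.85 v 0.85 × 1.08 = 0.918.

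**Direction and size by formula.** Let τ be the true difference in SVR, δ the part not carried by the two recorded predictors, and m the fraction missing, similar in each arm. Observed outcomes show τ; imputed outcomes show about τ − δ. The estimate is then about (1 − m)τ + m(τ − δ) = τ − mδ.
- δ = 0: no bias at any m.
- δ = +4 points, τ = 7.11 points (both assumed): m = 0.055, 0.11, 0.22 and 0.33 give biases of −0.22, −0.44, −0.88 and −1.32 points, or 3%, 6%, 12% and 19% of τ.
- δ = −2 points, τ = 1.11: the bias is +0.11 to +0.66 points. The sign follows δ, so overstatement requires arm to lower SVR at given recorded adherence.

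**Finite-sample check.** This used 600 simulated trials of 1,500, with 10 imputations and about 15% missing. With a positive residual arm effect, the two-variable model is biased by −0.9 points on a true 7.5, and adding arm and site leaves −0.1. With a negative residual effect, the bias is +0.7 on a true −0.6, and then 0.0. With no residual effect, it is about 0 either way.

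**Intended mechanism with noisy adherence.** Protocol 11.1 says the interventions target adherence. Assume the whole effect runs through it, calibrated to 0.850 v 0.918 with 3:2:1 allocation (large-sample calculation, 2,000,000 participants, assumed coefficients). Missingness depends on completion and recorded adherence. Change in log RR with arm left out:

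| Reliability of recorded adherence | 5% missing | 12% missing | 25% missing |
|---|---|---|---|
| Exact | 0 | 0 | 0 |
| 0.9 | −1% | −1% to −2% | −3% |
| 0.7 | −2% | −5% | −10% |
| 0.4 | −4% | −9% | −17% |

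With arm in the model, the change is within about 1% of zero.

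**Does it change a conclusion?** SE of log RR = √[0.15/(250 × 0.85) + 0.082/(750 × 0.918)] = 0.0287. ln 1.08 = 0.0770, so z = 2.68. After 9% shrinkage: 0.0770 × 0.91 = 0.0700, RR 1.073, z = 2.44. Allowing crudely for 12% fewer observed outcomes, SE = 0.0287/√0.88 = 0.0306 and z = 2.29. Both remain above 1.96.

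**Site.** With assumed site differences in SVR, and missingness varying by site alike in all arms, omitting site alone moved the contrast by up to about 0.3 points. When the site pattern of missingness differed by arm, the two-variable model was off by −0.7 points, and adding site removed this.

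**The case against.** The strongest reply is that the two variables are the intended mediators. If they carry the effect and are recorded well, nothing is lost. The primary analysis is untouched, and separate analyses use censoring weights, randomisation as an instrument, and loss to follow-up by arm. All of this stands, and it is why the point is minor. It does not justify the restriction, because exact recording cannot be assumed.

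A reader might go further and infer that adherence is recorded differently by arm, so that the bias could favour Arm 3. SAP 3d plans an analysis "exclusively among participants assigned to Arm 3 (high intensity support) where weekly adherence data will be collected using biometric data", and Protocol 11.2.3 bases counts on bottles ("Participants will be asked to return their empty pill bottles at which time the number of pills remaining will be counted") while Arm 3 receives pill boxes. The documents do not support that inference. The biometric records are named for an additional analysis within Arm 3. The comparative definition in SAP 2b uses the same sources in every arm. Protocol section 9 applies surveys and pill counts at every pick-up, and in 11.1.3.1 Arm 3 participants who hold a week's supply bring their container. Differential recording is possible, but its presence and direction would be assumptions. The same holds for a material site effect.

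A further objection concerns the remedy. The near-complete removal of bias depends on missingness being explained by recorded variables. If it depends on true adherence, adding arm still leaves about −0.6%, −2.2% and −4.1% at reliability 0.9, 0.7 and 0.4 (12% missing). If it depends on SVR itself (assumed log-odds −1.5), adding arm leaves −20% to −22%, against −22% to −29% without it. This stands: the change helps in each case but is not a full cure.

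**Conclusion.** The stated rule omits the variable whose effect the check estimates, and it should be changed. The likely consequence is modest shrinkage: about 1% to 9% of the log RR at an assumed 12% missing, with full mediation and reliability 0.9 to 0.4. It is zero if completion and adherence are recorded exactly and carry the whole effect. The missing rate, the reliability and the size of any residual arm effect are all assumptions, since the documents give none of them. Arm is the main omission; leaving out site is expected to matter little unless site-related missingness differs by arm.

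Two larger conclusions do not follow. The shift alone does not overturn a planning-case result, and the missing-as-failure primary analysis is not affected. Nor should the sentence be read as pooling the risk strata: SAP sections 1 and 1e point the other way, so naming the stratum is a clarification. This is a minor, cheap improvement to one sensitivity analysis.

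**What to change.** In SAP 1b and Protocol 15.7.2.1, remove the restriction to two variables and state that missing SVR is imputed within each risk stratum from one model pooled over arms, with randomised arm and site as main effects alongside treatment completion and adherence, and with deaths kept as failures.

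Do not impute separately by arm with site terms. In the 250-person high-intensity arm of the minimal-risk stratum, at 95% SVR, 12% missing and seven equal sites, observed failures per site average 250 × 0.88 × 0.05 / 7 = 1.6. With about 31.4 observed people per site, the chance that at least one site has no failure is 1 − (1 − 0.95^31.4)^7 = 79%, and it is about 95% with 167 people. The logistic model would then often fail through separation. Pooled over arms, at 95% SVR in each, the average is 1,500 × 0.88 × 0.05 / 7 = 9.4 failures per site.

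The cost is a wording change in two documents and a slightly larger model. All the variables are already collected.

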15.4 Sample Size Considerations

The anticipated sample size for this trial is 3,000 with approximately 420 recruited at each site over an 18-24 month period. Approximately 15-20 persons per month per site will be recruited. Recruitment may be unbalanced across the sites due to larger client volume at some sites. Sample size calculations were based on the primary outcome: sustained virologic response (SVR) defined as HCV RNA < lower limit of quantification (LLOQ) 10 to 60 weeks after completion of treatment (cure) and an intention to treat analysis. The trial is defined for superiority assessment; however, if no statistically significant difference between support strategies is detected within a specific stratum, a lesser objective of interest is non-inferiority with a pre-specified non-inferiority margin.

ELEVATED RISK STRATUM	N=1500 total (750 high intensity, 500 medium intensity, 250 low intensity)		N=1225 total (intensity, 410 intensity, 200		N=1000 total (500 high intensity, 333 medium intensity, 167 low intensity)		
SVR in PWID	RR comparing RR comparing		RR RR comparing		RR	RR comparing	
receiving	high to low	high to medium	comparing	high to	comparing	high to	
low/medium	intensity	intensity	high to low	medium	high to low	medium	
intensity			intensity	intensity	intensity	intensity	
intervention							
0.80	1.09	1.08	1.10	1.08	1.11	1.09	
0.85	1.08	1.06	1.08	1.07	1.09	1.08	
0.90	1.06	1.05	1.06	1.05	1.07	1.06	
0.95	1.04	1.03	1.04	1.03	1.04	1.04	
MINIMAL RISK	N=1500 total (750 low		N=1225 total (N=1000 total (500 low		
STRATUM	intensity, 500 medium		intensity, 410		intensity, 333 medium		
	intensity, 250 high intensity)		intensity, 200 high intensity)		intensity, 167 high intensity)		
SVR in PWID	RR comparing	RR comparing	RR	RR comparing	RR	RR comparing	
receiving low	high to low	medium to low	comparing	medium to low	comparing	medium to low	
intensity	intensity	intensity	high to low	intensity	high to low	intensity	
intervention			intensity		intensity		
0.80	1.10	1.08	1.11	1.08	1.12	1.09	
0.85	1.08	1.06	1.09	1.07	1.09	1.08	
0.90	1.06	1.05	1.07	1.05	1.07	1.06	
0.95	1.04	1.03	1.04	1.03	1.05	1.04	

Table 15.4.1. Relative risk (RR) of sustained virologic response (SVR) across stratum of risk for treatment failure (elevated and minimal risk).

[figure not shown]

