At the Entry visit, prior to randomization and treatment initiation, each participant will undergo a short survey to capture information on barriers/facilitators to treatment adherence identified in the prediction model. Responses to this survey will be captured in an eCRF and integrated with other data from the EHR. The algorithm will be used to classify persons into two strata according to their propensity for HCV treatment failure (minimal or elevated risk).

Individuals will be preferentially randomized to the support level that matches their failure risk. Those at elevated risk for treatment failure will be randomized at an allocation ratio of 3:2:1 for high, medium and low intensity support respectively. Those at minimal risk will be randomized at a ratio of 1:2:3 to high, medium and low-intensity support, respectively.

Randomization will be integrated into the EHR. The Study Nurse who will complete the survey will receive the determination of study arm from an automated program. Both study staff and study participants will be blinded to the designation of minimal/elevated risk stratum.

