Adherence (secondary outcome). Adherence will be defined both using both self-reported data and objective data on refills completed and pill counts. It will be analyzed as both a continuous outcome (e.g., percentage of doses reported as taken; percentage of doses taken according to refills completed/pill counts) and a dichotomous variable (e.g., >90% of doses reported as taken; >90% of doses taken according to refills completed/pill counts). We will use both self-reported adherence as well as For the dichotomous adherence outcome, analyses will be conducted as they are specified for the primary outcome. For the continuous variable, the analysis will compare the percentage value of adherence across level of support (low, medium, high intensity) within the two strata of risk. Using a linear regression model, in the elevated risk stratum, the difference in adherence level for those who received the low and moderate intensity interventions will be compared to those who received the high intensity intervention. In this analysis, adherence will be calculated based on the data from the surveys at 4, 8 and 12 weeks. The comparisons will be adjusted only for site. For those at minimal risk of failure, analyses will be similar.

Per protocol analysis. We will conduct a per protocol analysis which will exclude individuals who died or were lost to follow-up before the end of treatment or who discontinued treatment prematurely.

Sensitivity Analyses. We will conduct sensitivity analyses as outlined in the Statistical Analysis plan similar to those described for the primary outcome include those to account for missing data due to missed visits. Specifically, we will use fully specified conditional specification multiple imputation of the SVR outcome based on available adherence reports.

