their extensions (Poisson regression with robust variance estimation) with adjustment for site as a fixed effect. For the continuous variable, the analysis will compare the percentage value of adherence across level of support (low, medium, high intensity) within the two strata of risk. Using a linear regression model, in the elevated risk stratum, the difference in adherence level for those who received the low and moderate intensity interventions will be compared to those who received the high intensity intervention with adjustment for site. For those at minimal risk of failure, analyses will be similar except comparing the high and medium intensity interventions to the low intensity interventions. In this analysis, adherence will be calculated based on the data from the surveys at 4, 8 and 12 weeks as well as all medication dispensation records. In the primary intent to treat approach, all those randomized will be included regardless of whether treatment was completed or on treatment visits were missed.

2b.1. Per protocol analysis. We will conduct a per protocol analysis which will exclude individuals who died or were lost to follow-up before the end of treatment or who discontinued treatment prematurely.

2b.2. Sensitivity analyses.

- Regression models will be repeated considering site as a random effect (instead of as a fixed effect).¹
- Regression models will be repeated without adjustment for site.
- To account for covariates that are differentially distributed by arm or prognostic for the outcome:
 - We will repeat the regression models described above adjusting for any baseline demographic and behavioral factors that are different by study arm within strata of risk.
 - We will repeat the regression models described above including a covariate for the prognostic score.
 - We will incorporate the covariates included in the prognostic score through application of the standardized estimator of Moore and van der Laan^{2,3} in the stratified analyses (minimal and elevated). This will allow us to estimate the average treatment effect (ATE) within strata contrasting the proportion of the population that would achieve SVR in the groups of interest.
- To account for missing data
 - We will use fully conditional specification multiple imputation of the adherence outcome based on available reports and treatment completion data.

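### The linear model for continuous adherence names no variance estimator; with 3:1 and 1:3 arms, the default high-versus-low intervals are miscalibrated if spread differs by arm

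*SAP*

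**What the plan says.** SAP 2b treats adherence both as a percentage and as a dichotomy at 90%, each from self-report and from refill and pill-count data. For the percentage: "Using a linear regression model, in the elevated risk stratum, the difference in adherence level" is estimated between the lower-intensity arms and the high-intensity arm, adjusted for site. In the minimal-risk stratum the reference becomes the low-intensity arm. Protocol 15.7.2.2 gives the same model and adds: "The comparisons will be adjusted only for site". Neither text says how the standard error is computed.

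For the dichotomy, SAP 2b uses log-binomial models or "their extensions (Poisson regression with robust variance estimation) with adjustment for site as a fixed effect". SAP section 1 has the parallel wording for SVR: "Using log-binomial models (or their extensions, i.e., Poisson regression with robust variance estimation) including adjustment for site as a fixed effect". Robust variance is therefore attached to the Poisson fallback and is not mentioned for the linear model.

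On allocation, protocol 15.5 says: "Those at elevated risk for treatment failure will be randomized at an allocation ratio of 3:2:1 for high, medium and low intensity support respectively". It continues: "Those at minimal risk will be randomized at a ratio of 1:2:3 to high, medium and low-intensity support, respectively". Table 15.4.1 in protocol 15.4 plans the elevated stratum as "N=1500 total (750 high intensity, 500 medium intensity, 250 low intensity"; the minimal stratum mirrors it.

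**The concern.** Default linear regression estimates one residual variance for all arms. With equal arms that does little harm even when spreads differ. With a 3:1 split the pooled variance is dominated by the large arm, while the true uncertainty comes mostly from the small one, so the interval is wrong unless the spreads match.

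Unequal spread is plausible here. Adherence runs from 0 to 100% (protocol 12.3.10). Hypotheses 3 and 3a (protocol 7.3) expect more support to raise it, and hypotheses 2 and 2a expect more support to raise completion. SAP 2b keeps everyone randomized in the analysis whether or not they completed treatment. An arm with fewer early stoppers would sit nearer the ceiling and have a shorter low tail. Because the allocation is mirrored, the same pattern of spread would push the error in opposite directions in the two strata. At stake are the high-versus-low intervals for hypotheses 3 and 3a.

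**Working it through.** **Inputs from the plan.** Stratum size is 1500. 1500 × 3/6, 2/6 and 1/6 gives 750, 500 and 250, which matches Table 15.4.1. As a check on the planning basis, the pooled two-proportion formula (two-sided 0.05, 80% power, comparator SVR 85%) gives detectable relative risks of 1.075 and 1.062, against the stated 1.08 and 1.06. The documents give no SD, power or interval width for continuous adherence, so there is no figure of the plan's own to reproduce on that outcome.

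**Assumed input.** The ratio of the low-arm SD to the high-arm SD, varied from 0.67 to 2.

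**Formulas.**
- Pooled SE = √[ s_p² (1/n₁ + 1/n₂) ], with s_p² = [(n₁−1)s₁² + (n₂−1)s₂²]/(n₁+n₂−2)
- True SE = √( s₁²/n₁ + s₂²/n₂ )
- Actual coverage of a nominal 95% interval = 2Φ(1.96 × pooled SE / true SE) − 1

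**Worked case, SD 10 (high) and 15 (low).**
- Elevated, 750 high and 250 low: s_p² = (749×100 + 249×225)/998 = 131.2. Pooled SE = √(131.2 × 0.005333) = 0.836. True SE = √(100/750 + 225/250) = 1.017. Ratio 0.82, coverage 89.3%.
- Minimal, 250 high and 750 low: s_p² = (249×100 + 749×225)/998 = 193.8. Pooled SE = 1.017. True SE = √(100/250 + 225/750) = 0.837. Ratio 1.21, coverage 98.3%.

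**High versus low over the range.**

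| SD low / SD high | Elevated: SE ratio, coverage | Minimal: SE ratio, coverage |
|---|---|---|
| 0.67 | 1.21, 98.3% | 0.825, 89.4% |
| 1 | 1.00, 95% | 1.00, 95% |
| 1.25 | 0.90, 92.1% | 1.12, 97.1% |
| 1.5 | 0.82, 89.3% | 1.21, 98.3% |
| 2 | 0.73, 84.9% | 1.36, 99.2% |

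**The 3:2 comparisons in two-arm models, lower-intensity SD 1.5 times larger.** Elevated high versus medium: ratio 0.93, coverage 93.0%. Minimal medium versus low: ratio 1.08, coverage 96.6%. At an SD ratio of 2 these become 91.8% and 97.3%.

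**One three-arm model instead** (low/high ratio 1.5, medium SD in between). High versus low covers 90.1% (elevated) and 97.8% (minimal). The 3:2 contrasts have SE ratios of 1.03 and 1.00.

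**Is a ratio of 1.25 to 2 reachable?** As an illustration only, let completers average 97% (SD 4) and stoppers be uniform on 0–90% (mean 45, variance 90²/12 = 675). With a proportion p of stoppers, the variance is 675p + 16(1−p) + p(1−p)×52². In the elevated stratum, 8% versus 15% stoppers gives SDs 16.4 and 21.4 (ratio 1.31, coverage 91%). With 5% versus 20% the SDs are 13.3 and 24.1 (ratio 1.81, coverage 86%).

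**Does a robust standard error cure it?** In simulation (bounded beta outcome, seven site fixed effects, 3000 runs, SDs 10 and 15), default coverage was 90.0% (elevated) and 98.2% (minimal). HC2 gave 95.4% and 95.3%. With the SDs reversed, the default gave 98.2% and 89.1%, and HC2 gave 95.2% and 94.3%.

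**The case against.** A reader might infer that the intervals will be too narrow in the elevated stratum and too wide in the minimal stratum. The documents do not support that as fact. It needs the low-intensity arm to be the more variable, and no SD is given for any arm. The stopper illustration suits a refill-based measure better than self-report on a visual analogue scale, where someone who stops attending gives no later report. SAP 2b does not say how such missing reports enter the analysis. Dispensing is weekly in Arm 3 and every 28 days in Arms 1 and 2, so measurement itself may affect spread. All of this stands: the direction is conditional.

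A reader might also infer that the SAP requires robust variance for every binary outcome and singles out the linear model. It does not. Robust variance is named only for the Poisson extension; the log-binomial model and the logistic GEE for HIV suppression carry no such statement. Nor does the text specify a pooled variance. That is inferred from silence, and a robust fit is not ruled out.

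The effect on conclusions may also be small. With identical distributions in the arms the test is valid. Under the stopper illustration, power is 95–100% with either standard error in three of four elevated corner cases, and 77% versus 69% (default versus robust) in the fourth. In the minimal stratum the cost of the default varies: about 74% versus 86% at 4% and 10% stoppers, but about 98% versus 99.5% at 5% and 15%. Adherence is a secondary outcome, and the 90% dichotomy gives a parallel reading.

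What the objection does not remove is the gap itself. None of the sensitivity analyses in 2b.2 is described as addressing unequal variance. Sample size does not help either, because the SE ratio depends on the allocation and SD ratios and hardly at all on N.

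**Conclusion.** The point holds in conditional form. Run with its default standard error, the stated linear model gives miscalibrated high-versus-low intervals for continuous adherence whenever the arms differ in spread. If the low-intensity arm is the more variable, which is plausible but assumed, coverage falls to roughly 85–92% in the elevated stratum and rises to roughly 97–99% in the minimal stratum for SD ratios of 1.25 to 2. At a ratio of 0.67 the pattern reverses, to about 98% and 89%. The 3:2 comparisons move by about 1 to 3 points, or hardly at all in a single three-arm model. The dichotomous adherence analysis and the primary SVR analysis are not affected. This is a worthwhile correction to a secondary analysis and does not threaten the trial's main result.

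**What to change.** In SAP 2b and protocol 15.7.2.2, state that the linear model for continuous adherence uses heteroscedasticity-consistent (HC2 or HC3) standard errors, for both the self-reported and the refill/pill-count versions. Apply the same to the regression repeats in SAP 2b.2 that do not use a random site effect.

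The cost is one phrase in each document and one software option. Data and point estimates do not change. Intervals widen wherever the smaller arm is the more variable one and narrow where the larger arm is. If the spreads prove equal, the results barely move.
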